4. STUDY DESIGN

4.1. Endpoints

Safety and tolerability endpoints

- Frequency of adverse events
- Incidence of adverse reactions to IMP
- Frequency of serious adverse reactions
- Emergence of treatment-emergent adverse events
- The frequency of treatment-emergent adverse events related to infusion rate
- The incidence of administration site reactions
- The frequency of clinically significant deviations in vital signs (blood pressure, body temperature, pulse rate and respiratory rate)
- The frequency of clinically significant deviations in laboratory findings (complete blood count, biochemical findings, markers of intravascular haemolysis, and coagulation parameters)

Safety data are also assessed separately in children and adolescents (after an interim assessment in adults) and compared with the adult data.

Primary pharmacokinetic endpoint:

Mean threshold (trough) plasma concentration of total IgG prior to the next administration of the product, when reaching steady state (after 4 months of treatment), assessed over 6 months.

Primary pharmacokinetic variable:

The monthly trough IgG levels, measured after 4 months of treatment with the IMP, prior to the next infusion, once every 4 weeks, over 6 months, did not fall below the trough levels of the previous therapy with SCIG or IVIG (BIOVEN).

Secondary pharmacokinetic endpoints

These endpoints are tested in the subgroup of subjects aged over 18 years who received treatment with BIOVEN prior to their enrolment in the study and, respectively, throughout the screening period:

- To confirm or calculate the IMP dose adjustment factor when converting from previous IVIG therapy with BIOVEN;

Tested in a subgroup of at least 20 adult patients with PID after approximately 4 months of treatment with the IMP BP-SCIG 20%:

- Area under the concentration-time curve (AUC)
- Maximum concentration (Cmax)
- Time to reach maximum concentration (Tmax)
- The threshold levels of total IgG during the dose titration phase (the dose-effect dependence)
- the *in vivo* elimination half-life
- the elimination constant
- serum clearance
- volume of distribution
- incremental recovery

Secondary endpoints are transformed into corresponding variables.

Primary efficacy endpoint:

Primary efficacy endpoint: The number of serious bacterial infections per subject per year (in order to achieve less than 1.0 infections/subject/year)

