9.5 Analysis of safety and tolerability parameters

a) Laboratory results (the indicators of complete blood count, serum chemistry and urinalysis). Compare the results of indicators at screening and at the last visit. Provide descriptive statistics for each laboratory indicator at time points T before treatment and T after treatment.

Determine the relative changes in quantitative variables based on their mean values from the following formula:

$$X(\%) = \frac{T_i - T_{\text{baseline}}}{T_{\text{baseline}}} \times 100,$$

where T_{baseline} is the arithmetic mean of the variable at baseline, and T_i is the arithmetic mean of the analysed variable at subsequent visits. Represent these changes over time as a plot.

For variables measured only twice according to the schedule of patient assessments (at baseline and after completion of the course of treatment), evaluate the significance of their changes in each group using either a t-test for paired data or a Wilcoxon signed rank test, depending on the normality of the distribution, the latter checked with Shapiro–Wilk’s test.

For the variables measured according to the schedule of patient assessments more often than twice, evaluate the changes in quantitative variables over time using a one-way analysis of variance (ANOVA) or rank analysis depending on the normality of the distribution, checked using the Shapiro–Wilk test. In this setting, the dependent variable is the parameter being analysed, and the “visit” factor is the fixed parameter. Evaluate the value and significance for the reliability of the difference between the visits using a contrast analysis (simple contrasts) or post hoc analysis with Tukey’s test (for ANOVA) or the Wilcoxon signed rank test with Holm’s adjustment (for the rank test). To verify the preconditions for the use of analysis of variance, the normality of distribution of the residuals will be tested using the Shapiro–Wilk test. If the residuals are not distributed normally, a corresponding rank analysis will be performed.

For each variable, plot the changes of mean values (when the distribution is normal) or median values (when the distribution is not normal) over time, for each group.

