Convert the variables measured on a continuous scale into categorical variables with the following two categories: “within normal” and “outside normal”. Perform an analysis of the converted variables using the methods of descriptive statistics (the frequency and percentage [%] in each group have been provided) and represent the distribution of categories as plots. Statistical inferences shall be made.

b) The results of HR, BP, RR and body temperature measurements.

Calculate descriptive statistics (n, arithmetic mean, standard deviation, the median and the percentiles, the minimum and maximum values – depending on the type of distribution) for each visit according to patient assessment schedule.

c) AE data.

Provide descriptive statistics (frequency and percentage for the group).

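### Section 9.5(a) and (b) contain no analysis that yields the two safety endpoints in 4.1, the frequency of clinically significant deviations in laboratory findings and in vital signs

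*Protocol*

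**What the plan says.** Protocol 4.1 lists among the safety endpoints "The frequency of clinically significant deviations in vital signs (blood pressure, body temperature, pulse rate and respiratory rate") and "The frequency of clinically significant deviations in laboratory findings (complete blood count, biochemical findings, markers of intravascular haemolysis, and coagulation parameters"). It also asks that safety data be assessed separately in children and adolescents and compared with the adult data.

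Section 9.5(a) opens with "Laboratory results (the indicators of complete blood count, serum chemistry and urinalysis"). For these it prescribes:
- a comparison of screening with the last visit;
- descriptive statistics before and after treatment;
- percentage change of the mean from baseline;
- a paired t-test or Wilcoxon test for two measurements, or ANOVA or rank analysis by visit for more than two;
- a categorical step, "Convert the variables measured on a continuous scale into categorical variables with the following two categories", namely within normal and outside normal, summarised by frequency and percentage.

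Section 9.5(b), on heart rate, blood pressure, respiratory rate and temperature, says "Calculate descriptive statistics (n, arithmetic mean, standard deviation, the median and the percentiles", plus minimum and maximum, for each visit. Section 9.5(c) gives frequency and percentage of adverse events in one line.

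**The concern.** An endpoint defined as a frequency of clinically significant deviations needs a rule for what counts as a deviation, a reference state, and a count. Section 9.5(a) counts, but against the reference range and without linking each value to the same patient's pre-dose category. Section 9.5(b) does not count at all. Someone following 9.5 as written could fill every table it asks for and still be unable to report either endpoint.

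This matters more than usual because the study is single-arm and uncontrolled. The patient's own pre-dose state is the only internal reference, and the categorical step does not use it. In a marginal table of percentages, patients who become abnormal and patients who normalise offset each other, and a long-standing abnormality looks the same as a new one.

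**Working it through.** The protocol gives no figure to reproduce; the check is whether endpoint and analysis match.

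**Side by side**

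| Element of the 4.1 endpoint | Laboratory, 9.5(a) | Vital signs, 9.5(b) |
|---|---|---|
| Clinically significant | Replaced by within/outside normal | No criterion |
| Frequency | Count of within/outside normal | No count |
| Link to pre-dose state | Group averages and tests of change only; none in the categorical step | None |
| Scope | CBC, chemistry, urinalysis; haemolysis markers and coagulation not named | All four signs |
| Children versus adults | Not stated | Not stated |

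Haptoglobin, the Coombs test and the coagulation panel are all in the schedule (Table 4.2.1), so tests for the unnamed groups are already planned.

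**Illustration 1: marginal percentages hide new cases.** N = 56 is from 4.2; the rates are assumptions. Let b be the share outside normal before treatment, r the share of those who normalise, and q the share newly outside among those normal before treatment. Then

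share outside afterwards = b(1 − r) + (1 − b)q.

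- With b = 0.20, r = 0.5, q = 0.10: 0.20 × 0.5 + 0.80 × 0.10 = 0.18. The table falls from 20% to 18% although 56 × 0.80 × 0.10 ≈ 4.5 patients are newly abnormal.
- If 20% are outside normal at both times, 56 × 0.20 = 11.2, so the same two percentages fit anything from 0 to about 11 new cases.
- With q = 0 and r = 0, b from 5% to 30% gives 5–30% outside normal with no new case.

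**Illustration 2: reference-range noise.** Assume each value has a 5% chance of lying outside its range with no drug effect. The blood volumes in 6.3.13 rise to 18 mL at Visits 5, 8, 11, 14 and 17, which is consistent with five on-treatment CBC and chemistry visits. For one parameter with independent visits, P(outside at least once) = 1 − 0.95^5 = 1 − 0.774 = 0.226. With normally distributed values and an equal correlation between visits of 0.5 it is 0.18, and at 0.8 it is 0.13. The range is 13–23%, or 56 × 0.13 ≈ 7 to 56 × 0.226 ≈ 13 patients. This applies if the count is taken as ever outside normal; 9.5 does not say whether it is per visit or over all visits.

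**Illustration 3: vital-sign summaries.** Assume SD 15 mmHg and 3 of 56 patients with a 40 mmHg rise. The visit mean moves by 3 × 40 / 56 = 2.1 mmHg, against a standard error of 15 / √56 = 2.0. The per-visit maximum may show an extreme value, but it gives no count and does not show how far that patient has moved from pre-dose.

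**The case against.** **The adverse event route.** This is the strongest objection. Section 8.1 makes a laboratory deviation an adverse event if it is new or worse than baseline and meets at least one of four criteria, one being the investigator's judgement of clinical significance. Section 8.2 requires clinically significant abnormalities of laboratory results or other tests arising on treatment to be adverse events, and excludes those detected before the first dose. Section 9.5(c) then counts adverse events. That is treatment-emergent logic, and it stands. A reader might infer that the plan cannot detect new harm; the documents do not support that.

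The route still does not deliver the endpoints. Clinical significance is only one of four qualifying criteria. Section 8.2 asks for signs and symptoms to be combined under the diagnosis where it is known, so a single deviation may not appear under its own name. The explicit rule in 8.1 covers laboratory findings; vital signs fall only under the general adverse event definition and the wording on other tests or examination findings. And 9.5(c) does not separate either group.

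**The analysis is richer than the categorical step.** A reader might also infer that laboratory values are analysed solely as inside or outside normal, or vital signs solely as means. Neither is so. Section 9.5(a) compares with baseline and tests change, and 9.5(b) includes median, percentiles, minimum and maximum. These describe the group's distribution and give no frequency of significant deviations.

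**Pooling across parameters.** One could obtain a much larger noise figure by asking how many patients have any abnormal value on any parameter. Section 9.5 does not pool parameters, so only the single-parameter figure is relevant. In a per-visit table, moreover, the same 5% noise would be visible before treatment.

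**Left to the SAP.** Table layout usually is, and a SAP may add shift tables. But the protocol itself fixes a two-category split and a vital-sign summary that do not match its own endpoints.

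**Conclusion.** The mismatch holds. Following 9.5(a) and (b) as written yields neither of the two frequency endpoints in 4.1. The gap is clearest for vital signs, which have no deviation count, no change from baseline and no explicit adverse event rule. For laboratory values, the reference range stands in for clinical significance, the pre-dose category is unused in the categorical step, and two of the four laboratory groups in the endpoint are not named.

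The consequence is limited. These are descriptive safety endpoints, no success decision rests on them, and new significant laboratory deviations still reach the adverse event table. The matter should be corrected, but it does not undermine the trial. The sizes shown (13–23% ever outside normal on one parameter with no drug effect; a fall from 20% to 18% that conceals about 4.5 new cases) rest on assumed rates, correlations and SD. The mismatch itself does not depend on them.

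**What to change.** In 9.5(a) and (b), state the endpoint analysis directly: the number and percentage of dosed patients, and the number of events, with a clinically significant deviation that is new or worse than the pre-dose state, per laboratory parameter and per vital sign. Name the haemolysis markers and the coagulation panel in 9.5(a). Say who judges clinical significance for vital signs and where it is recorded, as 8.1 does for laboratory values.

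Replace or supplement the two-category split with shift tables from the pre-dose category to the worst on-treatment category. Present all of this overall and separately for children and adolescents and for adults, as 4.1 requires.

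The cost is a wording change in 9.5, a few tables and slightly more programming. The laboratory and vital-sign measurements are already scheduled before and during treatment, so no extra visit or sample is needed.

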9.6 Assessment of pharmacokinetic data

Analysis of pharmacokinetic parameters.

The main pharmacokinetic parameters include:

1. AUC-t value. Steady-state area under the concentration-time curve (AUC) for the total IgG level shall be compared with the values for the prior therapy (BIOVEN) for the relevant patient cohorts.
2. Trough IgG levels. The monthly trough IgG levels obtained, measured after 4 months of treatment with the IMP, prior to the next infusion, once every 4 weeks, over 6 months, shall be compared with the trough levels for at least two prior infusions of the previous SCIG or IVIG product. For treatment-naïve patients, a descriptive comparison with the data in published literature (if available) is required.

Methods of descriptive statistics: n, arithmetic mean, standard deviation, the median and the percentiles, the minimum and maximum values (depending on the type of distribution), including the plotting of graphs and charts and methods of interval estimation.

To evaluate the significance of changes over time in the event of assessing the parameter at two visits (before and after) in the case of quantitative variables, the analysis will use Student's t-test for paired data or Wilcoxon signed rank test – depending on the results of checking the normality of the distribution of difference [after - before] using the Shapiro-Wilk test. In order to assess changes over time in the event of measuring variables at more than two visits, methods of one-way analysis of variance (ANOVA) with subsequent application of post hoc analysis using Tukey's test will be used. In order to compare by those variables, by which the data were heterogeneous at baseline, covariance analysis (ANCOVA) will be used. In order to check the preconditions for the use of analyses of variance and covariance, the normality of distribution of the data and their residuals will be tested using the Shapiro-Wilk test. If the residuals are not distributed normally, or if the data do not pass the normality check, a corresponding rank analysis will be performed.

For the Shapiro-Wilk test, the significance level will be set at 0.01, and for other tests it will be set at 0.05. If a multiple comparisons effect occurs, significance level adjustments will be applied using the Holm method or Benjamini-Hochberg method.

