“Clinical trials of medicinal products involving a minor or a child may be conducted only if the relevant medicinal product is intended for the treatment of paediatric diseases or if the purpose of the clinical trial is to optimise the dosing or regimen of the medicinal product accordingly for children or minors” and on other aforementioned data, a paediatric population **may** be included in this clinical study without prior full completion of clinical trials involving competent adult subjects.

As part of this clinical study, all patients will receive the investigational medicinal product BP-SCIG 20%, solution for subcutaneous administration, manufactured by BIOPHARMA PLASMA LLC subcutaneously.

The IMP BP-SCIG 20% will be administered at the frequency of once a week for 52 weeks, subcutaneously using a CRONO S-PID4 infusion pump, at the dose of 0.1–0.2 g/kg once a week (the dose over 4 weeks is 0.4–0.8 g/kg).

The dosing regimen shall be designed to achieve a minimum IgG level (at least 5–6 g/L), which will be measured monthly before each IMP infusion.

Efforts must be taken to maintain serum IgG within the reference range for the corresponding age group of patients.

Individual dose selection and adjustment may be required for each patient, depending on the pharmacokinetic response (IgG level) and clinical response. Threshold levels must be assessed in combination with the incidence of infectious episodes.

Dose adjustment of the IMP BP-SCIG 20% based on threshold IgG levels is performed by the Investigator based on the clinical presentation of each individual patient.

A loading dose of IMP may be required (at the Investigator’s decision): at least 0.2–0.5 g/kg (1.0–2.5 mL/kg) of body weight per week. This dose is distributed across several days, with a maximum daily dose of 0.1 to 0.15 g/kg.

After achieving a steady-state (minimal) level of IgG, maintenance doses are administered at repeated intervals (approximately once a week) to achieve a cumulative monthly dose of 0.4–0.8 g/kg. Each single dose must be administered to different anatomical locations.

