5.1. Inclusion Criteria

Table 5.1.1 – Inclusion criteria for CT subjects

No.	Inclusion criterion
1.	a signed informed written consent of the patient/patient's parents or legally authorised representative to take part in the study;
2.	children from 0 to 18 years of age, of both sexes; or adult patients: males and females older than 18 years;
3.	a diagnosis of primary immunodeficiency with impaired antibody production document-supported according to the ESID criteria, requiring replacement therapy with immunoglobulins;
4.	patients with a body weight of no less than 9.1 kg;
5.	patients who received replacement therapy with intravenous immunoglobulin (IVIG) products at intervals from 21 to 28 days at the dose of 0.4–0.8 g/kg, for at least 4 months prior to the start of the study and have total serum IgG levels ≥ 5 g/L*, which is confirmed by the results of no less than 2 measurements performed immediately before the scheduled IVIG administration after signing the ICF, or patients who received replacement therapy with subcutaneous immunoglobulin (SCIG) products at the dose of 0.4–0.8 g/kg per month, for at least 4 months prior to the start of the study, and have total serum IgG levels ≥ 5 g/L*, based on the results of no less than 2 measurements performed immediately before the scheduled SCIG administration after signing the ICF; or patients with a newly established diagnosis of PID who have not yet received replacement therapy with IgG products (treatment-naïve patients) and have a serum IgG level ≤ 4 g/L;
6.	absence of episodes of serious bacterial infections (bacteraemia or sepsis, bacterial meningitis, osteomyelitis/septic arthritis, bacterial pneumonia, visceral abscess) while taking the previous medicinal product and absence of episodes of hospitalisation for at least 3 months prior to inclusion in the study and during the screening period (prior to the first administration of the IMP BP-SCIG 20%);
7.	a negative pregnancy test (in female patients with childbearing potential); readiness to use reliable methods of contraception throughout the study period;
8.	patient's ability, in the Investigator's judgement, to comply with all the requirements of the study protocol.

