6. TREATMENT OF SUBJECTS

6.1. Treatment regimen

The IMP shall be administered subcutaneously.

All patients will receive the investigational medicinal product BP-SCIG 20%, solution for subcutaneous administration manufactured by BIOPHARMA PLASMA LLC.

The IMP BP-SCIG 20% shall be administered at the frequency of once a week for 52 weeks, subcutaneously using a CRONO S-PID4 infusion pump.

The dosing regimen shall be designed to achieve a trough IgG level (at least 5–6 g/L), which will be measured before the next infusion.

Efforts must be taken to maintain serum IgG within the reference range for the corresponding age group of patients.

Individual dose selection and adjustment may be required for each patient, depending on the pharmacokinetic response (IgG level) and clinical response. Threshold levels must be assessed in combination with the incidence of infectious episodes. To reduce the risk of infection, it may be necessary to increase the dose and aim to achieve higher trough IgG levels.

A loading dose of IMP may be required (at the Investigator's decision): at least 0.2–0.5 g/kg (1.0–2.5 mL/kg) of body weight. This dose is distributed across several days, with a maximum daily dose of 0.1 to 0.15 g/kg.

After achieving a steady-state (minimal) level of IgG, maintenance doses are administered at repeated intervals (approximately once a week) to achieve a cumulative monthly dose of 0.4–0.8 g/kg. Each single dose must be administered to different anatomical locations.

Since the bioavailability of SCIGs is 30 % lower than that of IVIGs, partly due to binding to the extracellular matrix and cleavage by tissue enzymes (Wang et al. 2008; Berger et al. 2013), a dose adjustment factor of 1.37 will be used to convert the IVIG dose to the SCIG dose. This is based on historical data for bioequivalence evaluation of these administration routes (Wasserman et al. 2010, 2011; Berger et al. 2011) and meets the requirements of the US Food and Drug Administration (US FDA), according to which the SCIG doses must be adjusted to ensure an equivalent AUC for total IgG compared to previous IVIG therapy. Dose calculation for patients who received IVIG prior to the start of their participation in the study (John W Sleasman et al. 2019):

The initial dose of SCIG

$$\text{IgG} = \frac{\text{Previous IVIG dose (in grams)} \times 1.37}{\text{Number of weeks between IVIG administrations}}$$

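### Section 9.6 compares AUC on BP-SCIG with AUC on BIOVEN without the dose ratio each adult received, so it tests the 1.37 factor only in adults still dosed at 1.37

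*Protocol*

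**What the plan says.** Protocol section 3 lists, under the primary objective, confirming the adjustment factor so that steady-state AUC is non-inferior to BIOVEN. Section 4.1 makes confirming or calculating the factor a secondary pharmacokinetic endpoint. Section 4.2 says the BIOVEN profile will be used to confirm or recalculate it. No formula is given.

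Section 9.6 states the analysis: steady-state AUC "shall be compared with the values for the prior therapy (BIOVEN) for the relevant patient cohorts". For a quantity measured before and after, it names a "t-test for paired data or Wilcoxon signed rank test". It sets the Shapiro–Wilk level at 0.01, "and for other tests it will be set at 0.05".

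On dosing, section 6.1 uses 1.37 to set "The initial dose of SCIG". It then says: "Individual dose selection and adjustment may be required for each patient, depending on the pharmacokinetic response (IgG level) and clinical response". It adds: "To reduce the risk of infection, it may be necessary to increase the dose and aim to achieve higher trough IgG levels". Section 2.4 gives the weekly dose as 0.1–0.2 g/kg, which is 0.4–0.8 g/kg over four weeks. Section 5.1 admits patients on IVIG "at intervals from 21 to 28 days at the dose of 0.4–0.8 g/kg". Sections 2.2, 2.4 and 6.1 allow the factor to be modified after an interim PK analysis. The BP-SCIG profile is taken at Week 21 (section 4.2).

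**The concern.** A conversion factor relates two doses. An AUC ratio shows whether the factor was right only if the dose ratio behind it is known. Section 9.6 takes the AUC ratio and leaves the dose ratio out, while the dosing rules let that ratio move away from 1.37 before AUC is measured.

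The error can go either way. A cohort dosed below 1.37 can fall short of BIOVEN although 1.37 is correct. A cohort titrated upwards can match BIOVEN although 1.37 is too low. The second case matters more, because titration follows the IgG level and so tends to hide an inadequate starting factor. The factor sets the starting dose of patients who switch from IVIG.

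**Working it through.** **1. The plan's own figure.** Sections 2.4 and 6.1 say SCIG bioavailability is 30% lower than IVIG and take 1.37 from historical data. A 30% reduction gives 1/0.70 = 1.43, and 1.37 corresponds to 1/1.37 = 0.73, or 27% lower. The two agree only roughly. The historical data are not in the document, so 1.37 can be neither reproduced nor refuted.

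**2. The relation.** Assume linear kinetics and, for now, no endogenous IgG. Let R be the weekly SCIG dose divided by the weekly IVIG dose, F the relative bioavailability, and A the AUC ratio per unit time. Then A = R × F, and the factor needed is 1/F = R/A. This equals apparent SC clearance divided by IV clearance. A = 1 supports 1.37 only when R = 1.37.

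**3. The dose range** (sections 2.4, 5.1, 6.1). The largest IVIG dose at which 1.37 stays within 0.2 g/kg/week is 0.2 × weeks/1.37:
- 4-weekly: 0.2 × 4/1.37 = 0.584 g/kg; (0.8 − 0.584)/0.4 = 54% of the eligible range lies above this.
- 3-weekly: 0.2 × 3/1.37 = 0.438 g/kg; (0.8 − 0.438)/0.4 = 91% lies above.

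If the range overrides the formula and 1.37 is exactly right (F = 1/1.37):

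| IVIG dose and interval | Highest R | A = R/1.37 | R/A |
|---|---|---|---|
| 0.6 g/kg, 4-weekly | 0.8/0.6 = 1.33 | 0.97 | 1.37 |
| 0.8 g/kg, 4-weekly | 0.8/0.8 = 1.00 | 0.73 | 1.37 |
| 0.6 g/kg, 3-weekly | 0.6/0.6 = 1.00 | 0.73 | 1.37 |
| 0.8 g/kg, 3-weekly | 0.6/0.8 = 0.75 | 0.55 | 1.37 |

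A falls with the cap, while R/A recovers 1.37 each time. If 0.4–0.8 g/kg in section 5.1 is meant per month, only the 4-weekly figures apply.

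For a cohort with IVIG doses spread evenly over 0.4–0.8 g/kg (assumed) and limit L, the mean log ratio is [0.8 × ln(L/0.8) + (0.8 − L)]/0.4:
- 4-weekly: (−0.2518 + 0.2161)/0.4 = −0.089, giving 0.91.
- 3-weekly: (−0.4820 + 0.3620)/0.4 = −0.300, giving 0.74.
- Half of each: √(0.914 × 0.741) = 0.82.

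Over 0.4–0.6 g/kg, all 4-weekly, the ratio is 1.00 and the cap is negligible.

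**4. Titration (constructed example).** Suppose the AUC ratio at 1.37 is 0.80, so the factor needed is 1.37/0.80 = 1.71. Raising the dose by 25% gives A = 0.80 × 1.25 = 1.00. For IVIG 0.4 g/kg 4-weekly this moves the weekly dose from 0.4 × 1.37/4 = 0.137 to 0.171 g/kg, inside the range. The raw comparison reads parity, whereas R/A = 1.71/1.00 = 1.71.

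**5. Interim change (constructed example).** If half the adults read 0.80 at 1.37 and half read 1.00 at a corrected factor, the pooled ratio is √(0.80 × 1.00) = 0.89. That describes neither factor.

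**6. What the 0.05 paired test would do.** These simulations assume 10 adults and a within-patient CV of 15–20%. Ranges cover CV and raw or log scale. In the even-spread capped cohorts, with 1.37 correct, a difference is found in about 12–18% (4-weekly), 33–48% (half) and 65–84% (3-weekly) of studies. In the titration example, detection falls from 58–85% to about 5%. These are illustrations, not estimates for this trial.

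**7. Limit of the correction.** Total IgG includes the patient's own. If that share is 30% (assumed), the 0.8 g/kg 4-weekly case reads A = 0.3 + 0.7 × 0.73 = 0.81, and R/A = 1.00/0.81 = 1.23 instead of 1.37. The estimate is pulled towards the dose ratio given, but less far off than the raw reading.

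**8. Precision.** With CV 20% and 10 adults, the SD of the log ratio is √2 × √ln(1.04) = 0.280 and the standard error 0.280/√10 = 0.0886. The 95% half-width is 2.262 × 0.0886 = 0.200, so an estimate of 1.37 would have limits of about 1.12 to 1.67. With CV 15% they are about 1.18 to 1.59.

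**The case against.** The strongest reply is that section 9.6 does what the objective literally asks, which is to compare AUC with BIOVEN, and that turning this into a factor is detail for an analysis plan not shown. Sections 4.1 and 4.2 already promise to calculate or recalculate the factor, which cannot be done without doses. Clearance, which uses dose, is computed per patient in section 9.7. Section 9.6 offers ANCOVA, and section 4.2 allows analysis by covariates. Part of this stands: the planned data suffice, and an unseen plan may make the correction. But nothing in the protocol ties dose to the factor, and the protocol itself fixes both the AUC comparison and the dosing rules that separate it from 1.37.

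The numbers also draw fair objections. The initial-dose formula carries no cap, and the protocol does not say which rule prevails. Titration aims at a trough of at least 5–6 g/L and at clinical response, not at AUC parity, and IVIG patients enter with troughs of at least 5 g/L. A uniform 25% rise and an even interim split are constructions. All of this stands, so the sizes are conditional.

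A reader might go further and infer that raw AUC says nothing about 1.37, or that most of the cohort will be capped. The documents support neither. In adults still at 1.37 times their IVIG dose at Week 21, raw AUC is direct evidence. The IVIG dose mix is not given.

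**Conclusion.** The point holds in a limited form. The raw AUC comparison validly tests achieved exposure. It tests 1.37 only in adults whose Week 21 dose is still 1.37 times their IVIG dose, and the protocol provides three ways for that to fail: titration, the dose range and an interim change of factor.

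The thresholds of 0.584 and 0.438 g/kg follow from the protocol's own figures, provided the range overrides the formula. The AUC ratios also assume linear kinetics. The cohort ratios of 0.91, 0.82 and 0.74 add an assumed even dose spread, and the rejection rates add an assumed CV. How far this trial's result would be distorted cannot be estimated from the document. The change is worth making because confirming the factor is a stated primary aim and the better calculation uses data already planned.

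**What to change.** In section 9.6, for each adult with a BIOVEN profile:
- report the paired AUC ratio per unit time (the BP-SCIG profile covers 7 days, the BIOVEN profile 21–28) together with the actual weekly SCIG/IVIG dose ratio at the Week 21 profile;
- estimate the needed factor as dose ratio divided by AUC ratio, and summarise it over all such adults with a confidence interval;
- state that it is approximate because total IgG includes the patient's own.

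Keep the raw AUC comparison as the test of achieved exposure. If the factor is modified, show results by factor in force descriptively only. Restricting the judgement of 1.37 to adults dosed with it is unnecessary, because the corrected estimate uses everyone, and it would discard data from an already small cohort.

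The cost is wording and a little more analysis, with no new visits or samples. Section 4.9 already records prior IVIG dose and schedule and the home SCIG doses. Because the Week 21 infusion is given on site, confirm that its dose also reaches the eCRF. The downside is a wide interval with 8–10 adults.
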